### **7.      DISCONTINUATION OF STUDY TREATMENT AND PARTICIPANT DISCONTINUATION OR WITHDRAWAL**

Study and site closure is described in [Appendix 1](#).

## 7.1 DISCONTINUATION OF STUDY TREATMENT

It may be necessary for a participant to permanently discontinue (definitive discontinuation) study treatment. If study treatment is definitively discontinued, the participant will remain in the study follow-up phase. See the schedule of activities (see Section 1.3, [Table 2](#)) for data to be collected at the time of discontinuation of study treatment and for any further follow-up evaluations that need to be completed.

Participants must permanently discontinue study treatment if any of the following criteria are met:

- Any medical condition that the investigator determines may jeopardize the participant's safety if *the participant* continues to receive study treatment
- Investigator determination that treatment discontinuation is in the best interest of the participant
- Pregnancy
- Disease progression per RECIST v1.1
- Loss of clinical benefit as determined by the investigator after an integrated assessment of radiographic and biochemical data, local biopsy results (if available), and clinical status (e.g., symptomatic deterioration such as pain secondary to disease)
- Use of any anti-cancer therapy not allowed per protocol or use of a prohibited therapy (see Section [6.8.3](#))
- Intolerable toxicity related to study treatment, including development of an immune-mediated adverse event determined by the investigator to be unacceptable given the individual participant's potential response to therapy and severity of the event

The primary reason for study treatment discontinuation must be documented on the appropriate eCRF.

Participants will return to the clinic for a treatment discontinuation visit within 30 days after the final dose of study drug or within 30 days from the date the decision was made to permanently discontinue study treatment.

See the schedule of activities in Section 1.3 ([Table 2](#)) for details on follow-up assessments to be performed for participants who permanently discontinue study treatment. If a participant requests to be withdrawn from study treatment and/or follow-up, this request must be documented in the source documents and signed by the investigator.

### **7.1.1        Liver Chemistry Stopping Criteria**

Discontinuation of study treatment is required by the investigator when a study participant meets abnormal liver tests as outlined in Section [A3-7.7](#), or if the investigator believes that it is in best interest of the participant to discontinue.

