### A3–7.7 ABNORMAL LIVER FUNCTION TESTS

The finding of an elevated ALT or AST ( $>3 \times \text{ULN}$ ) in combination with either an elevated total bilirubin ( $>2 \times \text{ULN}$ ) or clinical jaundice in the absence of cholestasis or other causes of hyperbilirubinemia is considered to be an indicator of severe liver injury (as defined by Hy's Law). Therefore, investigators must report as an adverse event the occurrence of either of the following:

- Treatment-emergent ALT or AST  $>3 \times \text{ULN}$  in combination with total bilirubin  $>2 \times \text{ULN}$
- Treatment-emergent ALT or AST  $>3 \times \text{ULN}$  in combination with clinical jaundice

The most appropriate diagnosis or (if a diagnosis cannot be established) the abnormal laboratory values should be recorded on the Adverse Event eCRF (see Section [A3–7.2](#)) and reported to the Sponsor immediately (i.e., no more than 24 hours after the investigator becomes aware of the event), either as a serious adverse event or an adverse event of special interest (see Section [A3–5](#)).

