**Table A6-2 Criteria for Treatment Continuation in Arm A During the Maintenance Phase**

	Lurbinectedin	Atezolizumab
	Day 1	Day 1
ANC	$\geq 1.5 \times 10^9/L$ for participants of non-African descent or $\geq 1.3 \times 10^9/L$ for participants of African descent	No defined requirements
Platelets	$\geq 100 \times 10^9/L$	No defined requirements
Hemoglobin a	$\geq 9 \text{ g/dL}$	
Total bilirubin (or direct bilirubin)	$\leq 1.5 \times \text{ULN}$ For participants with known Gilbert disease: total bilirubin $\leq 3 \times \text{ULN}$	
AST/ALT	$\leq 2.5 \times \text{ULN}$ For participants with documented metastatic liver disease, AST and ALT levels $\leq 5 \times \text{ULN}$	
Serum creatinine	$\leq 1.5 \times \text{ULN}$ or creatinine clearance $\geq 30 \text{ mL/min}$	
TSH b	No defined requirements	Within normal range If TSH is above ULN, T4 must be within normal range
Muscular toxicity (myalgia, muscular weakness, CPK increase, rhabdomyolysis)		Grade 1 or better
Immune-related toxicities (colitis, pneumonitis, endocrinopathies c and others)	No defined requirements	Grade 1 or better
Other non-hematological drug-related adverse events (except increased GGT, amylase/lipase, nausea and vomiting, alopecia, asthenia, dermatologic events, and/or neuropathy d )		Grade 1 or better

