## Appendix 6: Safety Plan: Management of Identified and Potential Risks

**Table A6-4 Lurbinectedin Management Guidelines for Liver Abnormalities**

Severity of Transaminase (ALT or AST) Elevations by NCI CTCAE	Management
Grade 1 or 2	

• Dose reduction is usually not required.

• Consider discontinuing concomitant hepatotoxic medications and adding supportive care as indicated.

Grade $\geq 3$	

• Interrupt lurbinectedin and consider more frequent monitoring of ALT and/or AST.

• Restart lurbinectedin at a reduced dose when AST and ALT <math>\leq 2.5 \times</math> ULN (or for participants with documented metastatic liver disease, AST and ALT levels <math>\leq 5 \times</math> ULN).

• Discontinue if laboratory abnormalities cannot be reversed despite interruption of lurbinectedin.

NCI CTCAE = National Cancer Institute Common Terminology Criteria for Adverse Events; ULN = upper limit of normal.

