## Appendix 6: Safety Plan: Management of Identified and Potential Risks

Action to be Taken with Atezolizumab: Treatment with atezolizumab may be withheld or permanently discontinued because of toxicities, as specified below. If atezolizumab is withheld, treatment can be resumed if the event resolves to Grade 1 or better, or when symptoms improve as specified below. As a general rule, atezolizumab can be withheld for up to 12 weeks after event onset. Treatment with atezolizumab may be resumed if the event improves to Grade ≤1 within 12 weeks and if corticosteroids have been reduced to ≤10 mg/day oral prednisone or equivalent within 12 weeks. If atezolizumab is withheld for >12 weeks (or 4 cycles) of initiating steroids, the participant will be discontinued from atezolizumab. If an event does not resolve to Grade 1 or better while withholding atezolizumab, permanently discontinue atezolizumab and contact the Medical Monitor. Resumption of atezolizumab may be considered in patients who are deriving benefit and have fully recovered from an immune-mediated event, except when resumption of atezolizumab is expressly prohibited as described below. The decision to rechallenge patients with atezolizumab should be based on the investigator's benefit-risk assessment and should be documented by the investigator. The Medical Monitor is available to advise as needed.			
Event	Symptoms or CTCAE Severity Grade	Action to be Taken with Atezolizumab	Adverse Event Management [To Be Implemented in Combination with Above General Guidance]
Pulmonary event	Grade 1	
 
Continue with one exception: For pneumonitis, consider withholding and resuming on radiographic evidence of improvement.
 
	
 
Re-evaluate on serial imaging.
 
Closely monitor patients, including asymptomatic patients.
 

	Grade 2	
 
Withhold.
 
	
 
Consider bronchoscopy or BAL with or without transbronchial biopsy.
 
Initiate treatment with high-dose oral corticosteroids.
 

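### Section 7.1.1 requires study treatment to stop when the A3–7.7 liver tests are met, but Appendix 6, where the same cases are sent for management, has no branch for them and allows re-treatment after recovery

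*Protocol*

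**What the plan says.** **The stop.** Protocol Section 7.1.1, headed as liver stopping criteria and placed under Section 7.1 on discontinuing treatment, reads: "Discontinuation of study treatment is required by the investigator when a study participant meets abnormal liver tests as outlined in Section" A3–7.7. Section 3 defines study treatment as all protocol-mandated treatments, so in Arm A it covers both drugs.

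**The trigger.** Section A3–7.7 describes ALT or AST above 3 × ULN together with total bilirubin above 2 × ULN or clinical jaundice. Its lead sentence carries a condition: the finding "in the absence of cholestasis or other causes of hyperbilirubinemia is considered to be an indicator of severe liver injury". The action it then sets is reporting: "investigators must report as an adverse event the occurrence of either of the following", followed by two bullets for treatment-emergent values that do not repeat the condition.

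**Where management is said to be.** Section 8.3.8 lists these cases as adverse events of special interest and refers to Appendix 6 for their management.

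**What Appendix 6 says.**
- Lurbinectedin: Section A6–2.4.1.2 answers Grade 3/4 liver test increases with reduction or delay until recovery. Table A6-4, for Grade 3 or above, says to interrupt and then "Restart lurbinectedin at a reduced dose when AST and ALT" reach the table's recovery limits. It discontinues only if the abnormality cannot be reversed. Sections A6–2.2 and A6–2.3.1 allow treatment to go on beyond a 3-week delay where there is objective benefit.
- Atezolizumab: Table A6-5 continues at Grade 1, withholds at Grade 2 if the hepatic event lasts more than 5 days, and permanently discontinues at Grade 3 or 4. Its general rule is: "If atezolizumab is withheld, treatment can be resumed if the event resolves to Grade 1 or better, or when symptoms improve as specified below".
- Sections 6.1.2.1 and 6.5 let each drug be interrupted or discontinued separately. Section A6–2.3 lets each be interrupted separately.

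**The concern.** The protocol itself marks this combination as a sign of severe liver injury, and it gives two sets of instructions for it. One section says stop. The appendix that investigators are told to use for management never mentions that stop, and its lurbinectedin guidance leads to re-treatment once values recover. A site can follow Appendix 6 faithfully and still breach 7.1.1 by re-exposing the participant.

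Two further points are left open in 7.1.1. The first is whether both drugs must stop when only one is suspected, given that other sections treat the drugs separately. The second is whether the condition in the A3–7.7 lead sentence limits the stop. Two sites with the same participant, whose bilirubin is raised for another reason, could act in opposite ways.

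**Working it through.** No statistical figure in the plan bears on this, so the check sets the rules side by side.

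1. **Trigger against Table A6-4 (lurbinectedin).** The table is keyed to ALT/AST alone, in two rows: Grade 1 or 2, and Grade 3 or above. Together they cover every grade of elevation. Neither row has a bilirubin or jaundice condition, and neither makes discontinuation mandatory when the combination is met. The mismatch with 7.1.1 therefore exists at any grade and does not depend on CTCAE cut-offs.

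2. **Trigger against Table A6-2 (limits for re-dosing in Arm A).** The general limits are AST/ALT ≤ 2.5 × ULN and total bilirubin ≤ 1.5 × ULN. Since 2.5 < 3 and 1.5 < 2, a participant within them no longer meets the laboratory trigger. The conflict is thus about re-treatment after recovery: Appendix 6 provides for it and 7.1.1 does not.

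3. **Delay and benefit.** If the re-treatment criteria are not met after 3 weeks, A6–2.2 allows lurbinectedin to continue for objective clinical benefit with the sponsor's agreement. A6–2.3.1 allows it on the investigator's judgment, at a reduced dose. Section 7.1.1 has no such exception. The two appendix sections also differ on whose agreement is needed.

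4. **Section A6–2.1.** Its list of exceptions lets some rapidly reversible Grade 3 ALT/AST elevations continue without dose reduction. It does not mention the combined finding either.

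5. **Trigger against Table A6-5 (atezolizumab).** At Grade 3–4 the table permanently discontinues, which agrees with 7.1.1. A conflict arises only if an event meeting A3–7.7 is graded below 3 and is then continued, or withheld and resumed. The documents do not print the CTCAE cut-offs, so the frequency of that cannot be derived from them.

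6. **Size.** Section A6–1.1.2 reports no Hy's Law cases in the single-agent Phase II and III lurbinectedin studies. No denominator is printed there. Assume one common denominator N for the percentages in A6–1.1.2 and A6–1.1.4. Then 3 participants as 0.5% requires N > 3/0.0055 = 545.5, and 2 participants as 0.4% requires N ≤ 2/0.0035 = 571.4, so N is 546 to 571. Section 4.3.5 cites 554. With zero cases the approximate upper 95% bound is 3/N, which runs from 3/571 = 0.53% to 3/546 = 0.55%. Half of the SAP's target of 450 is 225 in Arm A, and 225 × 0.53% to 0.55% is about 1.2 participants. This is an upper bound for lurbinectedin alone, not a forecast, and it says nothing about atezolizumab.

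**The case against.** The best defence is that silence is not contradiction. Table A6-4 is a guide to transaminase elevations, 7.1.1 covers the specific combination, and a specific stopping rule can sit on top of general grade-based guidance. This would be persuasive if Appendix 6 pointed to 7.1.1. It does not, although 8.3.8 names it as the place for managing these very cases, so the defence relies on the site finding 7.1.1 unaided.

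Second, 7.1.1 does not use the word permanently, and the mandatory list in 7.1 has no liver criterion. This stands as a limit: permanence is inferred from the heading, the placement under 7.1, and Appendix 6's use of separate terms for interrupting and discontinuing. If a temporary stop was meant, the text should say so.

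Third, the A3–7.7 bullets are reporting instructions, and a reporting net may be wider than the definition behind it. That is fair, and A3–7.7 is not faulty as a reporting section. The gap is that 7.1.1 borrows it as a stopping rule without saying which part applies.

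Some stronger readings are tempting and are not supported:
- A reader might infer that lurbinectedin can restart whatever the bilirubin. Table A6-2 separately limits bilirubin before re-dosing.
- A reader might infer that Table A6-2 permits dosing while the trigger is still met. Its criteria are necessary conditions, not permission. On the laboratory values, overlap would need both of its wider allowances at once (liver metastases and Gilbert disease). The restriction to treatment-emergent values, the other-causes condition and the table's row on other drug-related events all undercut that case.
- A reader might infer that Table A6-5 conflicts throughout. It agrees with 7.1.1 at Grade 3–4.
- A reader might take the Grade 3/4 ALT or bilirubin rates in A6–1.1.2 as the number of cases affected. Those are isolated elevations, not the combination.

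**Conclusion.** The inconsistency is real and limited. It is clearest for lurbinectedin: 7.1.1 requires a stop without exception, while Appendix 6 leads to re-treatment after recovery and, in places, to continuation for benefit. For atezolizumab it is conditional on an event graded below 3. It is also unclear whether the stop covers one drug or both, and whether the cholestasis or other-causes condition applies.

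Few participants should be affected. The cited lurbinectedin studies had no Hy's Law cases, and the rough bound of about 1.2 in Arm A rests on an assumed common denominator and on single-agent data. Version 8 states that the cut-off for the final OS analysis has been reached, so the number still exposed to the conflict is smaller than the full arm. The primary estimands handle early discontinuation by treatment policy, so the primary analyses as defined do not change. The reason to act is participant safety and consistent conduct across sites. The conclusion assumes that discontinuation in 7.1.1 means a lasting stop, as its heading and placement suggest.

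**What to change.** Reconcile Sections 7.1.1, A3–7.7, A6–2.1 to A6–2.3 and A6–2.4.1.2 with Tables A6-2, A6-4 and A6-5. Add a row or footnote in Tables A6-4 and A6-5 for participants who meet A3–7.7, with a cross-reference to 7.1.1. The reconciled text should give one answer to each of three questions:

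- whether such a participant stops for good or may be re-treated after recovery, and whether the benefit exceptions apply;
- whether the rule covers one drug or both;
- whether the condition about cholestasis or other causes of raised bilirubin applies to the stop.

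The sponsor's clinical team decides which rule stands; this point takes no view on it. The cost is protocol wording only. ALT, AST and bilirubin are already in the chemistry panel scheduled each maintenance cycle in Table 2, so no new test is needed.

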### **7.2            PARTICIPANT DISCONTINUATION OR WITHDRAWAL FROM THE STUDY**

A participant may withdraw from the study at any time at his or her own request or may be withdrawn at any time at the discretion of the investigator for safety, behavioral, compliance, or administrative reasons.

The primary reason for discontinuation from the study should be documented on the appropriate eCRF. If a participant requests to be withdrawn from the study, this request must be documented in the source documents and signed by the investigator.

If a participant withdraws consent from the study, the Sponsor may retain and continue to use any data collected before withdrawal of consent. Samples collected prior to withdrawal may be analyzed, unless the participant specifically requests that the samples be destroyed (as documented in the source documents) or local laws require destruction of the samples. However, if samples have been tested prior to withdrawal, results from those tests will remain as part of the overall research data.

If a participant withdraws from the study, the study staff may use a public information source (e.g., county records) to obtain information about survival status.

### **7.3            PARTICIPANTS LOST TO FOLLOW-UP**

A participant will be considered lost to follow-up if he or she repeatedly fails to return for scheduled visits and is unable to be contacted by the study site.

The following actions must be taken if a participant fails to return to the clinic for a required study visit:

- The site must attempt to contact the participant and reschedule the missed visit as soon as possible and counsel the participant on the importance of maintaining the assigned visit schedule. If the participant is unable or unwilling to comply with study visits, site personnel should assess reasons the participant is unable or unwilling to return to the clinic, and determine if there are ways to support participant participation.
- Before a participant is deemed lost to follow-up, the investigator or designee must make every effort to regain contact with the participant (where possible, 3 telephone calls and, if necessary, a certified letter to the participant's last known mailing address or local equivalent methods). These contact attempts should be documented in the participant's medical record.
- Should the participant continue to be unreachable, he or she will be considered lost to follow-up.

## **8. STUDY ASSESSMENTS AND PROCEDURES**

Written informed consent for participation in the study must be obtained before performing any study-related procedures (including screening evaluations).

Informed Consent Forms for enrolled individuals and for individuals who are not subsequently enrolled will be maintained at the study site.

Study procedures and their timing are summarized in the schedule of activities (see Section 1.3 [[Table 1](#) and [Table 2](#)]). Protocol waivers or exemptions are not allowed.

Urgent safety concerns should be discussed with the Sponsor immediately upon occurrence or awareness to determine if the participant should continue or discontinue study treatment.

Adherence to the study design requirements, including those specified in the schedule of activities, is essential and required for study conduct.

All screening evaluations must be completed and reviewed to confirm that potential participants meet all eligibility criteria. The investigator will maintain a detailed record of all participants screened to document eligibility or record reasons for screening failure, as applicable.

Procedures conducted as part of the participant's routine clinical management and obtained before signing of the Informed Consent Form may be utilized for screening or baseline purposes provided the procedures meet the protocol-specified criteria and are performed within the time frame defined in the schedule of activities.

Medical history and baseline conditions, including clinically significant diseases, surgeries, cancer history (including prior cancer therapies and procedures), reproductive status, smoking history, and use of alcohol and drugs of abuse will be recorded at induction baseline. Any medication and/or vaccine (including over-the-counter or prescription medicines, vitamins, and herbal supplements) used by the participant within 7 days prior to enrollment will be recorded at induction baseline. Demographic data, including age, sex, and self-reported race or ethnicity, will also be recorded. At the time of each physical examination, an interval medical history should be obtained and any changes in medications and allergies should be recorded.

Participants will be closely monitored for safety throughout the study. Participants should be assessed for toxicity prior to each dose; treatment will be administered only if the clinical assessment and local laboratory test values are acceptable. Urgent safety concerns should be discussed with the Sponsor immediately upon occurrence or awareness to determine if the participant should continue or discontinue study treatment.

At applicable sites, certain study assessments may be performed by a mobile nursing (MN) professional at the participant's home or another suitable location, such as a local practice, to improve access and convenience for participants in the study. The Sponsor will evaluate and may select a health care company (the MN vendor) to provide MN services for participating sites. The MN vendor is responsible for ensuring that all MN professionals are licensed, qualified, and in good standing, as per applicable regulations, and that appropriate background checks have been performed. If the investigator at a participating site determines that MN services are appropriate for a participant and the participant gives written informed consent to participate in MN visits, the MN vendor will communicate with the participant and the participant's site. MN visits will be scheduled on specified visit days, to allow for relevant assessments to be performed by the MN professional. The schedule of activities (see Section 1.3 [[Table 1](#), [Table 2](#), and [Table 3](#)]) will specify the assessments that may be performed by a MN professional.

## **8.1 EFFICACY ASSESSMENTS**

### **8.1.1 Tumor and Response Evaluations**

A tumor assessment is required at induction screening and at maintenance screening. Participants must have SD or partial or complete response per RECIST v1.1 at maintenance screening in order to be eligible for randomization into the maintenance phase. Tumor assessments are to be performed during the maintenance phase every 6 weeks ( $\pm 7$  days) for 48 weeks following Cycle 1, Day 1 of the maintenance phase and every 9 weeks ( $\pm 7$  days) thereafter, regardless of treatment delays, until radiographic disease progression per RECIST v1.1, withdrawal of consent, death, or study termination by the Sponsor, whichever occurs first. Participants without any radiographic evidence of disease progression 2 years after Cycle 1, Day 1 of the maintenance phase may undergo tumor assessments every 3 months ( $\pm 7$  days) or more frequently if required per local standard of care until radiographic disease progression per RECIST v1.1, withdrawal of consent, death, or study termination by the Sponsor, whichever occurs first. Thus, tumor assessments are to continue according to schedule in participants who discontinue treatment for reasons other than disease progression per RECIST v1.1, even if they start new non-protocol anti-cancer therapy. At the investigator's discretion, tumor assessments may be repeated at any time if PD is suspected.

All measurable and/or evaluable lesions should be assessed and documented at screening. Tumor assessments performed as a standard of care prior to obtaining informed consent and within 28 days prior to enrollment do not have to be repeated at screening, so long as they meet criteria as per RECIST v1.1.

Study treatment will be continued until radiographic disease progression according to RECIST v1.1, unacceptable toxicity, or a participant's decision to discontinue, whichever occurs first.

The tumor assessment performed during maintenance screening will serve as the baseline scan (maintenance baseline) for RECIST v1.1 assessment purposes post-randomization.

The potential need for palliative radiotherapy should be considered, if possible, during the selection of target lesions as an irradiated target lesion renders the patient non-evaluable for RECIST v1.1 tumor response with the exception of the assessment of disease progression.

